9.5.2.2 Total Volume of Blood Sampling

Table 6 presents the number of blood samples and the total volume of blood that will be collected throughout the study. Additional samples may be taken at the discretion of the investigator if the results of any tests fall outside reference ranges or clinical symptoms necessitate testing to ensure subject safety.

Table 6	Summary of Blood Sample Volumes
---------	---------------------------------

	Sample Volume per Collection (mL)	Number of Collection Time Points	Total Volume Collected (mL)
Clinical laboratory tests	8.5	Screening (including pregnancy testing): 1 Baseline (Day -1): 1 Day 2: 1 Day 14 or early termination: 1	8.5×4=34
Viral test	8.5	Screening: 1	8.5×1=8.5
PK blood sampling	4	20	4×20=80
Blood sampling for plasma protein binding	12	2	2×12=24
Total			146.5

9.5.3 Appropriateness of Measurements

All clinical assessments are standard measurements commonly used in bioavailability studies.

The safety assessments to be performed in this study, including hematology analyses, blood chemistry tests, urinalysis, and assessment of AEs, are standard evaluations to ensure subject safety.

- 9.5.4 Reporting of Serious Adverse Events, Pregnancy, and Events Associated with Special Situations
- 9.5.4.1 Reporting of Serious Adverse Events

All SERIOUS ADVERSE EVENTS, regardless of their relationship to study treatment, must be reported on a completed SAE form by email or fax as soon as possible but no later than 24 hours from the date the investigator becomes aware of the event (revised per Amendment 01).

SAEs, regardless of causality assessment, must be collected through the last visit in the Treatment Phase and for 28 days after the subject's last dose. All SAEs must be followed to resolution or, if resolution is unlikely, to stabilization. Any SAE judged by the investigator to be related to the study treatment or any protocol-required procedure should be reported to the sponsor regardless of the length of time that has passed since study completion.

The detailed contact information for reporting of SAEs is provided in the Investigator Study File.

For urgent safety issues call: PPD (24/7 number).

For urgent safety issues, please ensure all appropriate medical care is administered to the subject and contact the appropriate study team member listed in the Investigator Study File.

It is very important that the SAE report form be filled out as completely as possible at the time of the initial report. This includes the investigator's assessment of causality.

Any follow-up information received on SAEs should be forwarded within 24 hours of its receipt. (revised per Amendment 01) If the follow-up information changes the investigator's assessment of causality, this should also be noted on the follow-up SAE form.

Preliminary SAE reports should be followed as soon as possible by detailed descriptions including copies of hospital case reports, autopsy reports, and other documents requested by the sponsor.

The investigator must notify his/her IRB/IEC of the occurrence of the SAE, in writing, if required by their institution. A copy of this communication must be forwarded to the sponsor to be filed in the sponsor's Trial Master File.

9.5.4.2 Reporting of Pregnancy and Exposure to Study Drug Through Breastfeeding

Any pregnancy in a female subject in which the estimated date of conception is either before the last visit or within 28 days of last study treatment or any exposure to study drug through breastfeeding during study treatment or within 28 days of last study treatment must be reported.

If an adverse outcome of a pregnancy is suspected to be related to study drug exposure, this should be reported regardless of the length of time that has passed since the exposure to study treatment.

A congenital anomaly, death during perinatal period, an induced abortion, or a spontaneous abortion are considered to be an SAE and should be reported in the same time frame and in the same format as all other SAEs (see Section 9.5.4.1).

Pregnancies or exposure to study drug through breastfeeding must be reported by fax or email as soon as possible but no later than 1 business day from the date the investigator becomes aware of the pregnancy. The contact information for the reporting of pregnancies and exposure to study drug through breastfeeding is provided in the Investigator Study File. The Pregnancy Report Form must be used for reporting. All pregnancies must be followed to outcome. The outcome of the pregnancy must be reported as soon as possible but no later than 1 business day from the date the investigator becomes aware of the outcome.

A subject who becomes pregnant must be withdrawn from the study.

- 9.5.4.3 Reporting of Events Association with Special Situations
- 9.5.4.3.1 REPORTING OF ADVERSE EVENTS ASSOCIATED WITH STUDY DRUG OVERDOSE, MISUSE, ABUSE, OR MEDICATION ERROR

AEs associated with study drug overdose, misuse, abuse, and medication error refer to AEs associated with uses of the study drug outside of that specified by the protocol. Overdose, misuse, abuse, and medication error are defined as follows:

Overdose	Accidental or intentional use of the study drug in an amount higher than the protocol-defined dose				
Misuse	Intentional and inappropriate use of study drug not in accordance with the protocol				
Abuse	Sporadic or persistent intentional excessive use of study drug accompanied by harmful physical or psychological effects				

Medication error Any unintentional event that causes or leads to inappropriate study drug use or subject harm while the study drug is in the control of site personnel or the subject.

All AEs associated with overdose, misuse, abuse, or medication error should be captured on the Adverse Event CRF and also reported using the procedures detailed in Section 9.5.4.1 even if the AEs do not meet serious criteria. Abuse is always to be captured as an AE. If the AE associated with an overdose, misuse, abuse, or medication error does not meet serious criteria, it must still be reported using the SAE form and in an expedited manner but should be noted as nonserious on the SAE form and the Adverse Event CRF.

9.5.4.4 Expedited Reporting

The sponsor must inform investigator and regulatory authorities of reportable events, in compliance with applicable regulatory requirements, on an expedited basis (ie, within specific time frames). For this reason, it is imperative that sites provide complete SAE information in the manner described above.

9.5.4.5 Breaking the Blind

Not applicable

9.5.4.6 Regulatory Reporting of Adverse Events

AEs will be reported by the sponsor or a third party acting on behalf of the sponsor to regulatory authorities in compliance with local and regional law and established guidance. The format of these reports will be dictated by local and regional requirements.

9.5.5 Completion/Discontinuation of Subjects

The investigator may withdraw the subject from the study at any time for safety or administrative reasons. A subject may elect to discontinue the study at any time for any reason. All subjects who discontinue the study are to complete the study's early discontinuation procedures indicated in the Schedule of Procedures/Assessments (Table 4).

The investigator will promptly explain to the subject involved that the study will be discontinued for that subject and provide appropriate medical treatment and other necessary measures for the subject. A subject who has ceased to return for visits will be followed up by mail, phone, or other means to gather information such as the reason for failure to return, the status of treatment compliance, the presence or absence of AEs, and clinical courses of signs and symptoms.

Subjects who discontinue early from the study will be discontinued for 1 of these primary reasons: AE(s), lost to follow-up, subject choice, withdrawal of consent, pregnancy, study terminated by sponsor, or other. In addition to the primary reason, the subject may indicate 1 or more of secondary reasons for discontinuation. Study disposition information will be collected on the Subject Disposition CRF.

A subject removed from the study for any reason may be replaced.

9.5.6 Confirmation of Medical Care by Another Physician (for Hepatic Impairment Subjects):

The investigator will instruct subjects to inform site personnel when they are planning to receive medical care by another physician. At each visit, the investigator will ask the subject whether he/she has received medical care by another physician since the last visit or is planning to do so in the future. When the subject is going to receive medical care by another physician, the investigator, with the consent of the subject, will inform the other physician that the subject is participating in the clinical study.

9.6 Data Quality Assurance

This study will be organized, performed, and reported in compliance with the protocol, SOPs, working practice documents, and applicable regulations and guidelines. Site audits may be made periodically by the sponsor's or the CRO's qualified compliance auditing team, which is an independent function from the study team responsible for conduct of the study.

9.6.1 Data Collection

Data required by the protocol will be collected on the CRFs and entered into a validated data management system that is compliant with all regulatory requirements. As defined by ICH guidelines, the CRF is a printed, optical, or electronic document designed to record all of the protocol-required information to be reported to the sponsor on each study subject.

Data collection on the CRF must follow the instructions described in the CRF Completion Guidelines. The investigator has ultimate responsibility for the collection and reporting of all clinical data entered on the CRF. The investigator or designee as identified on Form FDA 1572 must sign the completed CRF to attest to its accuracy, authenticity, and completeness.

Completed, original CRFs are the sole property of Eisai and should not be made available in any form to third parties without written permission from Eisai, except for authorized representatives of Eisai or appropriate regulatory authorities.

9.6.2 Clinical Data Management

All software applications used in the collection of data will be properly validated following standard computer system validation that is compliant with all regulatory requirements. All data, both CRF and external data (eg, laboratory data), will be entered into a clinical system.

9.7 Statistical Methods

All statistical analyses will be performed after the study is completed and the database is locked and released. Statistical analyses will be performed using WinNonlin and SAS software or other validated statistical software as required. Details of the statistical analyses will be included in a separate statistical analysis plan (SAP).

9.7.1 Statistical and Analytical Plans

The statistical analyses of study data are described in this section. Further details of the analytical plan will be provided in the SAP, which will be finalized before database lock.

9.7.1.1 Study Endpoints

The endpoints include the following PK parameters derived by non-compartmental analysis using the plasma concentration-time data of lemborexant and its metabolites:

C _{max}	Maximum plasma concentration
t _{max}	Time to reach maximum plasma concentration
AUC _(0-t)	Area under plasma concentration vs. time curve from time = 0 to time of last quantifiable concentration
AUC _(0-inf)	Area under plasma concentration vs. time curve from time = 0 to infinity
t _{1/2}	Terminal phase plasma half-life
CL/F	Apparent total body clearance (for lemborexant only)
Vz/F	Apparent volume of distribution (for lemborexant only)
AUC Metabolite Ratio	Ratio of $AUC_{(0-inf)}$ of individual metabolite to $AUC_{(0-inf)}$ of lemborexant, corrected for molecular weights
fu	Plasma protein unbound fraction
AUCu	AUC _(0-inf) values adjusted by unbound fraction in plasma (for lemborexant only)
CLu/F	Apparent clearance relative to the unbound plasma concentration based on AUCu (for lemborexant only)

The C_{max} , $AUC_{(0-t)}$, and $AUC_{(0-inf)}$ based on total exposures of lemborexant will be the primary PK endpoints. The rest of the parameters, including the PK parameters of the metabolites, will be secondary endpoints.

9.7.1.2 Definitions of Analysis Sets

The Safety Analysis Set is the group of subjects who dosed with the test drug and had at least 1 postdose safety assessment.

The Pharmacokinetic Analysis Set is the group of subjects who dosed with the test drug and had sufficient PK data to derive at least 1 PK parameter.

9.7.1.3 Subject Disposition

9.7.1.4 Demographic and Other Baseline Characteristics

Demographic and other baseline characteristics for the safety analysis set will be summarized for each treatment group using descriptive statistics. Continuous demographic and baseline variables include age, weight, height, BMI, and for subjects with hepatic impairment: MELD score and Child-Pugh classification; categorical variables include sex, ethnicity, and race.

9.7.1.5 Prior and Concomitant Therapy

All investigator terms for medications recorded in the CRF will be coded to an 11-digit code using the World Health Organization Drug Dictionary (WHO DD, March 2017). Prior medications will be defined as medications that stopped before the dose of study drug. Any medication (including OTC medications) or therapy administered to the subject during the study (starting at the date of informed consent) will be recorded on the Prior and Concomitant Medication CRF or Non-Pharmacological Procedures CRF. All medications will be presented in subject data listings.

9.7.1.6 Efficacy Analyses

Not applicable.

- 9.7.1.7 Pharmacokinetic, Pharmacodynamic, Pharmacogenomic, and Other Biomarker Analyses
- 9.7.1.7.1 PHARMACOKINETIC ANALYSES

The Safety Analysis Set will be used for individual plasma concentration listings. The PK Analysis Set will be used for summaries of plasma concentrations and for analyses, summaries, and listings of PK parameters.

The effect of hepatic impairment on the PK of lemborexant, the primary PK parameters based on total C_{max} , $AUC_{(0-t)}$, and $AUC_{(0-inf)}$ will be compared between the cohort of healthy normal controls and the cohorts of subjects with mild and moderate hepatic impairment as defined by Child-Pugh classes A or B. A general linear model of logarithmically transformed values with hepatic function class as a fixed effect will be utilized to estimate the geometric mean ratio (and two-sided 90% confidence intervals) of subjects with mild/normal and moderate/normal hepatic function. Similar statistical analyses will be conducted for the PK parameters of the metabolites and unbound lemborexant as secondary endpoints. Protein binding will be calculated for metabolites without any assessment of PK parameters.

Scatter plots of PK parameters of lemborexant and its metabolites versus Child-Pugh Score will be provided. The association between the primary PK parameters and Child-Pugh Score will be evaluated by regression analysis (the PK parameter as a dependent variable and Child-Pugh Score as an independent variable). Similar analyses will be performed for

MELD score, serum albumin, total bilirubin, and PT. Additionally, association between the PK parameters and liver transaminase levels will be performed, if deemed necessary.

Summary statistics will be generated for each of the PK parameters for each Child-Pugh class and healthy controls.

9.7.1.7.2 PHARMACODYNAMIC, PHARMACOGENOMIC, AND OTHER BIOMARKER ANALYSES

Not applicable.

9.7.1.8 Safety Analyses

An evaluation of safety will be performed on the Safety Analysis Set. Safety data that will be evaluated include AEs, clinical laboratory results, vital signs, and ECGs.

Treatment-emergent adverse events (TEAEs) will be summarized for each Child-Pugh class and healthy controls. Descriptive summary statistics (eg, mean, standard deviation [SD], median, minimum, maximum for continuous variables, and number and percent for categorical variables) including shift tables of the laboratory, vital signs, ECG parameters. Changes from Baseline for the clinical laboratory, vital signs and ECG parameters will be evaluated for each Child-Pugh class and healthy controls by time point.

9.7.1.8.1 EXTENT OF EXPOSURE

All subjects enrolled in the study will receive a single 10-mg dose $(1 \times 10 \text{ mg lemborexant tablet})$ in the morning after an overnight fast.

9.7.1.8.2 ADVERSE EVENTS

The AE verbatim descriptions (investigator terms from the CRF) will be classified into standardized medical terminology using the Medical Dictionary for Regulatory Activities (MedDRA). AEs will be coded to the MedDRA (Version 20.1 or higher) lower level term (LLT) closest to the verbatim term. The linked MedDRA preferred term (PT) and primary system organ class (SOC) are also captured in the database.

A treatment-emergent adverse event (TEAE) is defined as an AE that emerges during treatment, having been absent at pretreatment (Baseline) or

- Reemerges during treatment, having been present at pretreatment (Baseline) but stopped before treatment, or
- Worsens in severity during treatment relative to the pretreatment state, when the AE is continuous.

Only those AEs that were treatment emergent will be included in summary tables. All AEs, treatment emergent or otherwise, will be presented in subject data listings.

The TEAEs will be summarized by group. The incidence of TEAEs will be reported as the number (percentage) of subjects with TEAEs by SOC and PT. A subject will be counted

only once within a SOC and PT, even if the subject experienced more than 1 TEAE within a specific SOC and PT. The number (percentage) of subjects with TEAEs will also be summarized by maximum severity (mild, moderate, or severe).

The number (percentage) of subjects with TEAEs will also be summarized by relationship to study drug (Yes [related] and No [not related]).

Subject data listings of AEs, TEAEs leading to death, SAEs, and AEs leading to withdrawal will be provided.

9.7.1.8.3 LABORATORY VALUES

Laboratory results will be summarized using Système International (SI) units, as appropriate. For all quantitative parameters listed in Section 9.5.1.5.3, the actual value and the change from baseline to each postbaseline visit and to the end of treatment (defined as the last on-treatment value) will be summarized by visit and group using descriptive statistics. Qualitative parameters listed in Section 9.5.1.5.3 will be summarized using frequencies (number and percentage of subjects), and changes from baseline to each postbaseline visit and to end of treatment will be reported using shift tables. Percentages will be based on the number of subjects with both nonmissing baseline and relevant postbaseline results.

Laboratory test results will be assigned a low/normal/high (LNH) classification according to whether the value was below (L), within (N), or above (H) the laboratory parameter's reference range. Within-group comparisons for each laboratory parameter will be based on 3-by-3 tables (shift tables) that compare the baseline LNH classification to the LNH classification at each postbaseline visit and at the end of treatment.

Clinical laboratory results post baseline will be evaluated for markedly abnormal values.

Appendix 1 presents the Sponsor's grading for laboratory values that will be used to identify subjects with markedly abnormal laboratory values.

9.7.1.8.4 VITAL SIGNS

Descriptive statistics for vital signs parameters (ie, diastolic and systolic BP, pulse, respiratory rate, temperature, weight) and changes from baseline will be presented by day and time after dosing and group.

9.7.1.8.5 ELECTROCARDIOGRAMS

Shift tables will present changes from baseline in ECG interpretation (categorized as normal; abnormal, not clinically significant; and abnormal, clinically significant) to end of treatment.

9.7.2 Determination of Sample Size

A sample size of 8 subjects per each cohort of mild and moderate hepatic impairment, as defined by Child-Pugh classes A or B, is based on the recommendations in regulatory guidelines for a minimum number of subjects to be enrolled for moderate liver impairment

cohort (FDA, 2003). Additionally, from single-dose studies of the 10-mg tablet (E2006-A001-004, E2006-A001-005, and E2006-A001-008), the pooled between-subject standard deviations of logarithmically transformed C_{max} and $AUC_{(0-inf)}$ of lemborexant were 0.334 and 0.391 respectively. With a sample size of 8 subjects in each Child-Pugh category and at least 8 matched controls, a 2-sided 90% confidence interval (CI) for the ratio for $AUC_{(0-inf)}$ will extend 0.322 from the observed mean difference on the log scale.

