7.2.1 Study Design

The overall study design proposed, including the dose, regimen, number of healthy control subjects, endpoints, and analyses follows the recommendations from the latest guidelines by FDA and EMA on evaluation of PK in subjects with hepatic impairment (FDA, 2003; EMA, 2005).

The proposed study design includes the enrollment of patients with mild and moderate liver impairment (Child-Pugh class A and B respectively). Subjects with severe hepatic impairment (Child-Pugh class C) will be excluded from the study as outlined above.

The regulatory guidelines include a provision for use of a reduced, sequential study design, to evaluate the group of subjects with higher severity of liver impairment first (such as moderate liver impairment), and if no effect on PK is demonstrated, then these results could be extrapolated to the subjects with liver impairment of lesser severity. In the case of lemborexant, the reduced study design is considered to be unsuitable since a large effect in the moderate hepatic impaired subjects is expected based on the current disposition profile for lemborexant. This design would require subsequent investigation in mild hepatic impaired subjects to ensure clarity regarding lemborexant labeling.

The proposed study design includes 8 subjects per cohort of mild and moderate hepatic impairment and 8 matched control subjects, and will utilize an estimation-based approach to calculate the ratios of the geometric means rather than powering the study to test for a

specific difference in exposure between subjects with hepatic impairment and healthy controls. In addition, 90% CIs for the slope parameter of the relationship between Child-Pugh score and apparent clearance of lemborexant may provide additional indication of any effect (or lack of) on lemborexant PK. This analysis will take into account all subjects' data (N=24), thereby increasing the possibility to detect a relationship between severity of liver impairment and lemborexant PK.

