9 INVESTIGATIONAL PLAN

9.1 Overall Study Design and Plan

E2006-A001-104 is a multicenter, single dose, open-label, parallel-group study in subjects with mild and moderate hepatic impairment and matched (with regard to age [± 10 years], sex, and body mass index [BMI, $\pm 20\%$]) healthy control subjects. The study will enroll a total of 24 subjects, including 16 subjects with impaired hepatic function; 8 subjects each in Child-Pugh class A (mild) and B (moderate). At least 8 healthy subjects will be dosed as one control cohort to match (1:1) to the subjects with hepatic impairment in each Child-Pugh class with regard to age, sex, and BMI.

The study will consist of 2 phases: Prerandomization and Treatment. The Prerandomization Phase will include 2 study periods; Screening and Baseline (Day -1). The subjects will be admitted to the clinical facility on Day -1, remain confined to the clinic until Day 8, and then return to the clinical facility for additional PK sampling as outpatients until Day 14. In the event of early discontinuation of the subjects, the subjects with Child Pugh Class A and B (Cohorts A and B) and the matched controls (Cohort C) may be replaced.

On Day 1, the subjects will be administered a single 10-mg dose of lemborexant with approximately 240 mL of water in the morning after an overnight fast. The blood samples for PK assessments will be collected at prespecified intervals up to 312 hours postdose administration. The subjects will be discharged on Day 14 of the study. In addition, the blood samples for plasma protein binding assessments of lemborexant will be collected from each subject at 2 time points; approximately 1 hour and 24 hours postdose.

The end of the study will be the date of the last study visit for the last subject.

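### The planned 90% CI half-width of 0.322 comes from a normal multiplier; the planned three-cohort model with 24 subjects gives 0.336 at the same SD

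*Protocol*

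**What the plan says.** Protocol 9.7.2 (Determination of Sample Size) bases 8 subjects per impaired cohort first on a regulatory guideline minimum, then adds a precision statement. It takes 0.334 for log Cmax and 0.391 for log AUC(0-inf) as the between-subject SDs, pooled from three earlier single-dose studies. For 8 per impaired cohort and a minimum of 8 controls, it then gives a half-width for AUC(0-inf) only: the two-sided 90% interval "will extend 0.322 from the observed mean difference on the log scale". The synopsis and SAP section 4 carry the same statement. None of the three places names the multiplier or calls the figure approximate.

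The analysis that will produce the interval is in Protocol 9.7.1.7.1 and, in the same terms, SAP 6.15: "A general linear model of logarithmically transformed values with hepatic function class as a fixed effect will be utilized". It yields the mild/normal and moderate/normal ratios with their 90% limits. Protocol 9.1 gives the size: "The study will enroll a total of 24 subjects, including 16 subjects with impaired hepatic function". The remaining 8 are controls. Protocol 7.2.1 says the study "will utilize an estimation-based approach to calculate the ratios of the geometric means rather than powering the study".

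**The concern.** The sample-size statement and the analysis section describe different intervals. A half-width of 0.322 needs the SD to be known in advance. The planned model estimates the residual variance from the trial, so its interval uses a t multiplier, which is larger than the normal one at this sample size.

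The study is designed for estimation and states neither power nor an effect size. The half-width is therefore the only number in the documents that tells a reader how precise the comparison is expected to be, and as written it is slightly optimistic.

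**Working it through.** **Inputs**

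- SD of log AUC(0-inf): 0.391 (Protocol 9.7.2)
- Subjects per group in each comparison: 8 impaired and 8 controls (Protocol 9.7.2, with controls given as a minimum)
- Confidence level: 90%, two-sided, so 5% in each tail (Protocol 9.7.2)
- Total: 24 in three cohorts (Protocol 9.1)
- Model: one general linear model with a three-level class effect (Protocol 9.7.1.7.1, SAP 6.15)
- Scale: natural log (titles of the SAP statistical-analysis tables, 14.2.4.1 onward)

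**Step 1. Reproduce the stated figure.**

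Half-width = multiplier × SD × sqrt(1/n1 + 1/n2)

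Standard error = 0.391 × sqrt(1/8 + 1/8) = 0.1955

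Normal multiplier: 1.6449 × 0.1955 = 0.3216, which rounds to 0.322.

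None of the alternatives tried gives 0.322:

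| Variant | Half-width |
|---|---|
| t, 21 df | 0.336 |
| t, 14 df (separate two-group model) | 0.344 |
| Paired t, 7 df | 0.370 |
| 95% normal | 0.383 |
| One-sided 90% normal | 0.251 |
| Cmax SD (0.334), normal | 0.275 |

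**Step 2. Apply the planned model.**

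Error df = 24 − 3 = 21, so t = 1.7207.

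Half-width = 1.7207 × 0.1955 = 0.3364

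Difference: 0.3364 − 0.322 = 0.014. Ratio: 0.3364 / 0.322 = 1.045.

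On the ratio scale, the limits are the observed ratio × 0.714 and × 1.400 with t, against × 0.725 and × 1.379 with the normal multiplier. An interval actually built with 1.645 at 21 df would cover about 88.5% rather than 90%.

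**Step 3. Look for a reading that rescues 0.322.**

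- *SD rounding.* SDs from 0.3905 to 0.3915 give 0.3360 to 0.3368 with t.
- *More controls.* With 9 controls (22 df): 1.7171 × 0.391 × sqrt(1/8 + 1/9) = 0.326. With 10 controls (23 df): 1.7139 × 0.391 × sqrt(1/8 + 1/10) = 0.318. It takes 10 controls, hence 26 subjects, to fall below 0.322. The stated figure also matches the normal formula only at exactly 8 controls; 9 would give 0.313.
- *Average half-width.* If the true SD is 0.391, the mean half-width over sampling of the SD is 0.9882 × 0.3364 = 0.332.
- *SD needed.* For t on 21 df to give 0.322, the observed SD would have to be 0.322 / (1.7207 × 0.5) = 0.374.

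**The case against.** The best defence is that 0.322 is a conventional planning approximation, correctly computed for a known SD, and that the documents never claim a t-based figure. It is also small against the uncertainty in the quantity itself. If the true SD is 0.391, the realised t-based half-width has a median of 0.331 and a 5th to 95th percentile range of 0.250 to 0.420. About 43% of such studies would come in at or below 0.322. The SD was pooled from three earlier single-dose studies, so its value in impaired subjects is an assumption in any case. No margin or decision rule uses 0.322, and the SAP already carries a post-database-lock addendum dated 24 July 2018, so the model's own interval supersedes any planning value.

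Most of this stands as a limit on importance. It does not make the sentence right. The text states the half-width outright, does not disclose an approximation, and refers to an interval that the plan takes from a fitted model. Sampling variation in the SD affects any planning figure; it does not change the multiplier the model uses, and the average half-width still exceeds 0.322.

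A further fair point is that the number of controls is left open as a minimum, so a corrected sentence should keep that wording and say what 0.336 is conditional on.

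**Conclusion.** The concern holds. At 8 subjects per cohort and an observed SD of 0.391, the planned model gives a half-width of 0.336, not 0.322. The stated precision is optimistic by 0.014 on the log scale, about 4.5%, or a factor of 1.40 instead of 1.38 either side of the ratio.

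The 0.336 rests on three assumptions:

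- **One model for all three cohorts.** This is the natural reading of both documents. Separate two-group models would give 0.344, further from the stated value.
- **Exactly 8 controls.**
- **An AUC(0-inf) from all 24 subjects.** SAP 6.2.3 lets this parameter go unreported when the terminal slope is judged unreliable. Any loss from the model would be expected to widen the interval.

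This is a correction to a planning statement. The cohort size has its own justification, the reported intervals will come from the model, and nothing in the design or analysis needs to change.

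**What to change.** In the synopsis, Protocol 9.7.2 and SAP section 4, replace the 0.322 statement with wording such as:

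*With 8 subjects in each impaired cohort and at least 8 matched controls, the two-sided 90% CI for the AUC(0-inf) ratio has a half-width of 0.336 on the natural-log scale (t, 21 df), a factor of 1.40 either side. This takes 8 controls (24 subjects in total), an AUC(0-inf) from every subject and an observed SD of 0.391.*

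The matching Cmax figure, 1.7207 × 0.334 × 0.5 = 0.287, may be added but is optional. If the sponsor prefers to keep 0.322, the minimum is to say that it is a normal approximation treating the SD as known.

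The cost is one number and its wording in three places, and a slightly less favourable precision statement. The sample size, the model and the reported intervals do not change. Because the database is already locked, the correction is documentary; Protocol 9.7.5 already provides for SAP revisions to be described in the clinical study report, which would be a suitable place to record it.
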